Both durvalumab and tremelimumab have well established toxicity profiles as a single agent and in combination. However, the combination of durvalumab tremelimumab and palliative radiation has not been previously studied, this study will include a formal safety analysis in the first 6 patients accrued. Enrollment will be halted until these first 6 patients complete the first two cycles of treatment (8 weeks), and are evaluable for acute toxicities (toxicities reported within the 1st 8 weeks after treatment initiation). Specifically, if 2 or more DLTs (Refer to Section 6.4) are observed, then, durvalumab dosing will be modified to 1500 mg IV Q6 weeks x 9 doses and tremelimumab 75mg IV Q6 weeks x 3 doses for the remaining 14 patients (fixed dosing for patients > 30kg). If 1 or fewer DLTs are observed, then an additional 14 patients will be enrolled and treated at the initial dose and schedule of durvalumab and tremelimumab. Patients in the run in phase who experience DLTs will undergo dose modifications described in Appendix 1.

Toxicities will be graded based on CTCAE v. 4 and summarized as the number and percentage of patients with each type of toxicity. Responses will be summarized as frequencies and percentages. The Kaplan Meier method will be used to estimate overall survival and progression free survival. Outcomes will be calculated from the date of study entry to the date of the corresponding event.

We will use multivariate statistics to test the hypotheses that pretreatment intratumoral immune cell phenotype and PD-L1 expression predict response to therapy, and that therapy alters systemic immunophenotype.

Sample Size Determination:

There are multiple ongoing studies in various tumor types exploring the activity of durvalumab and tremelimumab. In a published report of the combination in patients with advanced NSCLC treated on a phase Ib study, Grade 3-4 toxicity was observed in 17% of patients. Similarly, in single institution reports of SBRT with the monoclonal antibody, grade 3 or higher toxicity was reported in 6-16% of patients. With a 20 patient accrual goal, toxicity rates can be estimated to within 22% with 95% confidence. Any toxicity with at least 10% prevalence has at least an 87% chance of being observed. This design allows us to reasonably exclude a clinically significant increase in toxicity with the addition of radiation therapy to the durvalumab and tremelimumab combination as defined by the upper bound of the confidence interval.

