Patients treated with doses of tremelimumab above 1 mg/kg had a higher rate of adverse events (AEs), including discontinuations due to AEs, serious AEs (SAEs), and severe AEs. Between the 10 mg/kg durvalumab + 1 mg/kg tremelimumab and 10 mg/kg durvalumab + 3 mg/kg tremelimumab cohorts treated at the q2w schedule, the number of patients reporting any AE, Grade 3 AEs, SAEs, and treatment-related AEs was higher in the 10 mg/kg durvalumab + 3 mg/kg tremelimumab cohort than the 10 mg/kg durvalumab + 1 mg/kg tremelimumab cohort. A similar pattern was noted in the q4w regimens, suggesting that, as the dose of tremelimumab increased above 1 mg/kg, a higher rate of treatment-related events may be anticipated. Further, the SAEs frequently attributed to immunotherapy, pneumonitis and colitis, were more commonly seen in cohorts using either 3 or 10 mg/kg of tremelimumab compared to the 1-

mg/kg dose cohorts. Together, these data suggest that a combination using a tremelimumab dose of 1 mg/kg appeared to minimize the rate of toxicity when combined with durvalumab. As a result, all combination doses utilizing either the 3 or 10 mg/kg doses of tremelimumab were eliminated in the final dose selection.

In contrast, cohorts assessing higher doses of durvalumab with a constant dose of tremelimumab did not show an increase in the rate of AEs. The data suggested that increasing doses of durvalumab may not impact the safety of the combination as much as the tremelimumab dose. Further, safety data between the 10-mg/kg and 20-mg/kg cohorts were similar, with no change in safety events with increasing dose of durvalumab.

In Study D4190C00006, of all treatment cohorts, the cohort of 11 patients treated in the 20 mg/kg durvalumab + 1 mg/kg tremelimumab group had the fewest AEs, Grade ≥ 3 AEs, SAEs, and treatment discontinuations due to AEs, but still showed strong evidence of clinical activity. This cohort had a lower number of treatment-related Grade ≥ 3 AEs or treatment-related SAEs. No dose-limiting toxicities were reported.

Preliminary clinical activity of the durvalumab and tremelimumab combination did not appear to change with increasing doses of tremelimumab. The 15- and 20-mg/kg durvalumab q4w cohorts demonstrated objective responses at all doses of tremelimumab, and increasing doses of tremelimumab did not provide deeper or more rapid responses.

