(polymyositis and an uncoded event of neuromuscular disorder [VT]); the Grade 4 event of myasthenia gravis and Grade 5 polymyositis occurred in 1 subject. There were 2 subjects (both in the MEDI4736 20 mg/kg + tremelimumab 3 mg/kg Q4W cohort) with dose-limiting toxicities (DLTs): 1 subject with Grade 3 increased AST, and 1 subject with Grade 3 increased amylase and Grade 4 increased lipase. Fifty-six subjects (54.9%) reported SAEs, with events occurring in > 5% of subjects being colitis (9.8%) and diarrhea (7.8%). Thirty-six subjects (35.3%) experienced treatment-related SAEs. Twenty-seven subjects (26.5%) permanently discontinued treatment due to AEs. Treatment-related AEs resulting in discontinuation in ≥ 2 subjects were colitis (7 subjects), pneumonitis (5 subjects), diarrhea (3 subjects), and increased AST (2 subjects). Additional safety results from this study are presented in Section 1.3.1 and the durvalumab IB.

In the literature (**Error! Reference source not found.**), using the combination of the same class of drugs (eg, anti-PD-1 and anti-CTLA4 antibodies), specifically nivolumab + ipilimumab in a study involving patients with malignant melanoma, the safety profile of this combination had shown occurrences of AEs assessed by the Investigator as treatment-related in 93% of treated patients, with the most frequent events being rash (55% of patients), pruritus (47% of patients), fatigue (38% of patients), and diarrhea (34% of patients). Grade 3 or 4 AEs, regardless of causality, were noted in 72% of patients, with Grade 3 or 4 events assessed by the Investigator as treatment-related in 53%. The most frequent of these Grade 3 or 4 events assessed by the Investigator as treatment-related include increased lipase (in 13% of patients), AST (in 13%), and ALT levels (in 11%). Frequent Grade 3 or 4 selected AEs assessed by the Investigator as treatment-related in the combination therapy included hepatic events (in 15% of patients), GI events (in 9%), and renal events (in 6%). Isolated cases of pneumonitis and uveitis were also observed.

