3.3 Study Oversight for Safety Evaluation

The primary endpoint of this study is safety and tolerability. Durvalumab and tremelimumab will be given at the recommended fixed dosing in patients > 30kg (see section 1.3.1), which has been shown to result in minimal toxicity, but encouraging efficacy in NSCLC patients. Since the concurrent administration of radiation therapy is previously unstudied in this cohort, the first 6 patients will represent a run-in phase, and enrollment will be halted until all patients complete

the first two cycles of treatment (8weeks) These 6 patients will be assessed for DLTs and will determine if a modified dosing schedule of durvalumab and tremelimumab will be applied in the expansion phase.

In keeping with the study primary endpoint, a stopping rule will be implemented in the unlikely event that the combination under study is deemed to have unacceptably high toxicities. Enrollment will be halted if more than 3 patients experience a Grade 4 or higher drug related toxicity (CTCAE v. 4) during the trial or up to 30 days after the last investigational drug infusion. The likelihood of observing 3 or more Grade 4+ drug-related DLTs is 80% if the true rate is 20% and the likelihood is 91% if the true rate is 25%. This rule has an 83% chance of stopping in the 1st 10 patients if the true rate is 40%. Section 10.2.2 provides some guidelines on the attribution of toxicity to the drug and radiation combination. The study will be reviewed by the University of Washington/Fred Hutchinson Cancer Research Center Data Safety and monitoring board.

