6.2. Dosage and Administration

The treatment to be used in the run in phase of this trial for patients > 30kg is outlined in the Table below:

Drugs	Dose/Potency	Dose Frequency	Route of Administration	Regimen/Treatment Period
1. Durvalumab	1500 mg	Q4 weeks	IV infusion	Maximum of 13 doses
2. Tremelimumab	75mg	Q4 weeks	IV infusion	Maximum of 4 doses

If 2 or more DLTs (defined in Section 6.4) are observed in the run-in phase, the following treatment will be used for the remaining 14 patients to be treated on the clinical trial protocol:

Drugs	Dose/Potency	Dose Frequency	Route of Administration	Regimen/Treatment Period
1. Durvalumab	1500 mg	Q6 weeks	IV infusion	Maximum of 9 doses
2. Tremelimumab	75mg	Q6 weeks	IV infusion	Maximum of 3 doses

Patients who experience a DLT in the run in phase, will have dose interruptions/modifications as outlined in Appendix 1.

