6.4 Definition of DLT

Dose-limiting toxicities (DLTs) will be evaluated during the run in phase consisting of the first 6 patients enrolled in this trial. The period for evaluating DLTs will be from the time of first administration of durvalumab or tremelimumab until 28 days (cycle 1). Adverse event monitoring will continue for these subjects throughout the course of their treatment (beyond cycle 1) as outlined in the Schedule of Study Assessments, these adverse events will include potential XRT related toxicities. Subjects who do not remain on the study up to this time for reasons other than DLT will be replaced with another subject. Grading of DLTs will follow the guidelines provided in the Common Terminology Criteria for Adverse Events (CTCAE) version 4.0.

A DLT will be defined as any Grade 3 or higher toxicity that occurs during the DLT evaluation period. Toxicity that is clearly and directly related to the primary disease or to another etiology is excluded from this definition. The following will be DLTs:

- Any Grade 4 irAE
- Any \geq Grade 3 colitis
- Any Grade 3 or 4 noninfectious pneumonitis irrespective of duration
- Any Grade 2 pneumonitis that does not resolve to \leq Grade 1 within 3 days of the initiation of maximal supportive care
- Any Grade 3 irAE, excluding colitis or pneumonitis, that does not downgrade to Grade 2 within 3 days after onset of the event despite optimal medical management including systemic corticosteroids or does not downgrade to \leq Grade 1 or baseline within 14 days
- Liver transaminase elevation $> 8 \times$ ULN or total bilirubin $> 5 \times$ ULN
- Any \geq Grade 3 non-irAE, except for the exclusions listed below
 - Grade 3 fatigue lasting \leq 7 days
 - Grade 3 endocrine disorder (thyroid, pituitary, and/or adrenal insufficiency) that is managed with or without systemic corticosteroid therapy and/or hormone replacement therapy and the subject is asymptomatic
 - Grade 3 inflammatory reaction attributed to a local antitumor response (eg, inflammatory reaction at sites of metastatic disease, lymph nodes, etc)
 - Concurrent vitiligo or alopecia of any AE grade
 - Grade 3 infusion-related reaction (first occurrence and in the absence of steroid prophylaxis) that resolves within 6 hours with appropriate clinical management

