14. DATA MANAGEMENT

The Protocol Director, or her designees, will prepare and maintain adequate and accurate participant case histories with observations and other data pertinent to the study. Original source documents should be transcribed to Case Report Forms (CRFs) and used to analyze the study data. Source documents include hospital records, clinical charts, laboratory and pharmacy records, and recorded electronic data.

All data required by the trial will be entered onto paper and electronic case report forms. Any corrections to data required into the paper case report forms must be made in such a way that the original entry is not obscured. Only designated study staff will enter data for study participants after study visits. Case report forms will be checked against source document data by study staff.

Patient records will be kept in a secure location at the University of Washington accessible only to research authorized personnel. The patient identity will be kept as confidential as possible as required by law. Except as required by law, the patient will not be identified by name, social security number, address, telephone number, or any other direct personal identifier. Study subjects will be assigned an ID code. Information about the code will be kept in a secure location and access limited to research study personnel. The results of this research study may be presented at scientific or medical meetings or published in scientific journals. However, the patient identity will not be disclosed. The patient's personal data which may be included in the investigator's database shall be treated in compliance with all applicable laws and regulations.

Trial oversight will be carried out by the protocol director, [name], and her research staff. They will meet weekly to review recently acquired data and adverse events. The data recorded within the research charts and protocol database is compared with the actual data that is available from the medical record and/or clinical histories. Data detailed in the research case report forms includes the nature and severity of all toxicities, which are also reported as described above.

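### The rule that two or more DLTs trigger the six-weekly schedule acts only after all six run-in patients are enrolled, so a run-in patient who starts after the second DLT is still assigned four-weekly dosing

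*Combined protocol and SAP*

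**What the plan says.** The run-in has one DLT-linked enrollment hold, after the sixth patient. The Synopsis states it ("Enrollment will be halted until these first 6 patients complete the first two cycles of treatment (8 weeks"), and Section 3.3 repeats it: "the first 6 patients will represent a run-in phase, and enrollment will be halted until all patients complete" two cycles.

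Section 6.2 sets Q4W as the treatment for the run-in. If there are two or more DLTs, it gives the Q6W table with the words "the following treatment will be used for the remaining 14 patients to be treated on the clinical trial protocol". For the run-in patients themselves, the Synopsis provides individual management only: "Patients in the run in phase who experience DLTs will undergo dose modifications described in Appendix 1".

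Under Section 6.4 the DLT period "will be from the time of first administration of durvalumab or tremelimumab until 28 days (cycle 1"). No text staggers the six patients, pauses accrual at the second DLT, or assigns Q6W to a run-in patient who has not yet started.

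**The concern.** A count of DLTs cannot fall. Once two are confirmed among patients 1 to 5, the choice of Q6W is settled, whatever happens to the patients still to come. As written, those patients are nevertheless assigned the schedule that the rule has given up, and their data can no longer change the choice. In theory this could affect four patients, if both of the first two have a DLT before the third starts.

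What is at stake is some additional drug exposure from the second dose onward in a few patients. It does not bear on the validity of the trial's estimates.

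**Working it through.** **Plan's own figure.** The documents give no operating characteristic for the six-patient run-in, so there is nothing to reproduce.

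**Exposure difference (Section 6.2 tables).**
- Through week 12, each drug: Q4W at weeks 0, 4, 8, 12 = 4 doses; Q6W at weeks 0, 6, 12 = 3 doses.
- Ceiling without progression or toxicity: durvalumab 13 v 9 doses, tremelimumab 4 v 3.
- The first 28 days are the same on both schedules.

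**What is known of the DLT rate.** In the lung cancer combination study, Section 1.3.1 says of the 11 patients at this dose: "No dose-limiting toxicities were reported". Section 1.4.2.3 covers all 102 subjects: "There were 2 subjects (both in the MEDI4736 20 mg/kg + tremelimumab 3 mg/kg Q4W cohort) with dose-limiting toxicities (DLTs"). The exact two-sided 95% upper bound for 0/11 is 1 − 0.025^(1/11) = 28%. For 2/102 the estimate is 2.0% (95% CI 0.2 to 6.9%). That study gave no radiation. The 17% used below is the Grade 3-4 figure from Section 11.3, which is not a DLT rate. All the rates below are therefore illustrative.

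**Bounds without an accrual assumption** (independent patients, at most one DLT each, no replacements).
- Threshold met in six: 1 − (1−p)^6 − 6p(1−p)^5. At p = 0.17: 1 − 0.327 − 0.402 = 0.271.
- Threshold met within the first five, the most often that a late entrant could arise: 1 − (1−p)^5 − 5p(1−p)^4. At p = 0.17: 1 − 0.394 − 0.403 = 0.203.
- If each patient were fully assessed before the next started, the mean number of late entrants would be Σ (6−k)(k−1)p²(1−p)^(k−2) over k = 2 to 5. At p = 0.17: 0.116 + 0.144 + 0.119 + 0.066 = 0.445. If all six start together it is 0.

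**With accrual.** The documents give no accrual rate, so 1 to 2 patients a month is assumed. The simulation used 1,000,000 trials per setting and Poisson accrual from day 0. In the table, DLT onset is uniform over 28 days and the DLT is known at once. Each range runs from 2 a month to 1 a month.

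| DLT rate | Threshold met in six | Met within first five | Mean late entrants | Chance of any |
|---|---|---|---|---|
| 2% | 0.6% | 0.4% | 0.005–0.006 | 0.3% |
| 5% | 3.3% | 2.3% | 0.03–0.04 | 1.6–1.9% |
| 10% | 11.4% | 8.1% | 0.11–0.14 | 6–7% |
| 17% | 27.1% | 20.3% | 0.29–0.36 | 14–17% |
| 30% | 58.0% | 47.2% | 0.7–0.9 | 36–41% |

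**Later confirmation.** Several DLT definitions in Section 6.4 need days of non-resolution or repeat testing. With onset on days 14 to 28 plus 3 to 14 days to confirm, the results are:
- 17% rate: mean 0.17–0.28, chance of any 9–14%.
- 5% rate: mean 0.016–0.028, chance of any about 1–1.5%.

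**Extremes at 17%.** Four late entrants occur in 1 to 2% of trials if DLTs are known at onset. With one patient every 2 days the mean falls to 0.02. Slower accrual, 0.5 a month, with later confirmation gives 0.35 and 17%.

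**The case against.** The strongest reply is that this is a preference about a deliberate fixed-size run-in. Six Q4W patients followed for 8 weeks describe the triplet better than two do, and two DLTs in six mean something different from five in six. That stands, and it is the real cost of the change.

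Patients are also protected individually. The Synopsis requires assessment before each dose, and Appendix 1 generally holds or stops drug for Grade 2 or higher events. A late entrant with meaningful first-cycle toxicity would usually be held before the second dose. This stands too and limits the harm, but it does nothing for a late entrant without toxicity, who simply continues on Q4W.

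Three stronger readings are tempting and not supported:
- A reader might infer that late entrants suffer avoidable first-cycle DLTs. They do not, because the schedules are identical until the second dose. For the same reason, the restriction of Q6W to the remaining 14 is as much the defect as the missing pause.
- A reader might infer that Q6W is known to be safer. No document shows this. Section 1.3.1 links toxicity to tremelimumab above 1 mg/kg, and both schedules give 75 mg.
- A reader might infer that nobody is watching. Section 14 says of the protocol director and research staff "They will meet weekly to review recently acquired data and adverse events", and a monitoring committee and discretionary termination are in place (Sections 13.2.1 and 13.3). What is missing is a trigger tied to the DLT count. The Section 3.3 stopping rule does not supply one: it needs more than 3 patients with Grade 4 or higher drug-related toxicity, and a Grade 3 DLT does not count toward it.

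**Conclusion.** The gap in the wording is real and its expected effect is small. A run-in patient who starts after the second confirmed DLT is assigned Q4W although the plan has by then committed to Q6W. The size rests on three assumptions that the documents do not settle: the DLT rate of the triplet, the accrual rate, and how soon a DLT is confirmed. Over 1 to 2 patients a month and both confirmation assumptions, expect about 0.17 to 0.36 late entrants and a 9 to 17% chance of any at a 17% DLT rate, and about 0.02 to 0.04 and 1 to 2% at 5%.

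The probability that the run-in meets its threshold is the same with or without the change (27.1% at a 17% rate). Late entrants on Q4W would still contribute to the overall safety endpoint. The change is worth making because it is cheap. The trial does not depend on it.

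**What to change.** Amend the Synopsis, Section 3.3 and Section 6.2 to say:
1. When a second DLT, counted as the existing rule counts it, is confirmed in the run-in, enrollment pauses for prompt safety review of the available data. No further 8-week hold is needed for the schedule decision.
2. Every patient who starts afterwards receives Q6W, so the reference to the remaining 14 patients becomes all remaining patients.
3. With 0 or 1 DLT, the six-patient, 8-week hold stays as it is.

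Run-in patients already on Q4W without a DLT would stay on it, as now.

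The cost is two or three sentences in an amendment and a thinner Q4W safety description if the run-in fails. In the extreme only two patients would have started Q4W, leaving up to 18 of 20 on Q6W, a schedule that has no run-in of its own under the current plan either.

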AUC _{0-28day}	Area under the plasma drug concentration-time curve from time zero to Day 28 post-dose
AUC _{ss}	Area under the plasma drug concentration-time curve at steady state
BICR	Blinded Independent Central Review
BoR	Best objective response
BP	Blood pressure
C	Cycle
CD	Cluster of differentiation
CI	Confidence interval
CL	Clearance
C _{max}	Maximum plasma concentration
C _{max,ss}	Maximum plasma concentration at steady state
CR	Complete response
CSA	Clinical study agreement
CSR	Clinical study report

Abbreviation special term	or Explanation
CT	Computed tomography
CTCAE	Common Terminology Criteria for Adverse Event
CTLA-4	Cytotoxic T-lymphocyte-associated antigen 4
C _{trough,ss}	Trough concentration at steady state
CXCL	Chemokine (C-X-C motif) ligand
DoR	Duration of response
EC	Ethics Committee, synonymous to Institutional Review Board and Independent Ethics Committee
ECG	Electrocardiogram
ECOG	Eastern Cooperative Oncology Group
eCRF	Electronic case report form
EDoR	Expected duration of response
EGFR	Epidermal growth factor receptor
EU	European Union
FAS	Full analysis set
FDA	Food and Drug Administration
GCP	Good Clinical Practice
GI	Gastrointestinal
GMP	Good Manufacturing Practice
hCG	Human chorionic gonadotropin
HIGRT	Hypofractionated Image Guided Radiotherapy
HIV	Human immunodeficiency virus
HR	Hazard ratio
IB	Investigator's Brochure
ICF	Informed consent form
ICH	International Conference on Harmonisation
IDMC	Independent Data Monitoring Committee
IFN	Interferon
IgE	Immunoglobulin E

Abbreviation special term	or Explanation
IgG	Immunoglobulin G
IHC	Immunohistochemistry
IL	Interleukin
ILS	Interstitial lung disease
IM	Intramuscular
IMRT	Intensity modulated radiotherapy
IMT	Immunomodulatory therapy
IP	Investigational product
irAE	Immune-related adverse event
IRB	Institutional Review Board
irRECIST	Immune-related Response Evaluation Criteria in Solid Tumors
ITT	Intent-to-Treat
IV	Intravenous
IVRS	Interactive Voice Response System
IWRS	Interactive Web Response System
mAb	Monoclonal antibody
MDSC	Myeloid-derived suppressor cell
MedDRA	Medical Dictionary for Regulatory Activities
MHLW	Minister of Health, Labor, and Welfare
miRNA	Micro-ribonucleic acid
MRI	Magnetic resonance imaging
NCI	National Cancer Institute
NE	Not evaluable
NSCLC	Non–small-cell lung cancer
OAE	Other significant adverse event
ORR	Objective response rate
OS	Overall survival
PBMC	Peripheral blood mononuclear cell
PD	Progressive disease

Abbreviation special term	or Explanation
PD-1	Programmed cell death 1
PD-L1	Programmed cell death ligand 1
PD-L2	Programmed cell death ligand 2
PDx	Pharmacodynamic(s)
PFS	Progression-free survival
PFS2	Time to second progression
PGx	Pharmacogenetic research
PK	Pharmacokinetic(s)
PR	Partial response
q2w	Every 2 weeks
q3w	Every 3 weeks
q4w	Every 4 weeks
q6w	Every 6 weeks
q8w	Every 8 weeks
QTcF	QT interval corrected for heart rate using Fridericia's formula
RECIST 1.1	Response Evaluation Criteria in Solid Tumors, version 1.1
RNA	Ribonucleic acid
RR	Response rate
RT-QPCR	Reverse transcription quantitative polymerase chain reaction
SAE	Serious adverse event
SAP	Statistical analysis plan
SAS	Safety analysis set
SBRT	Stereotactic ablative Body Radiotherapy
SD	Stable disease
SNP	Single nucleotide polymorphism
SoC	Standard of Care
sPD-L1	Soluble programmed cell death ligand 1
T ₄	Thyroxine

Abbreviation special term	or Explanation
TSH	Thyroid-stimulating hormone
ULN	Upper limit of normal
US	United States
WBDC	Web-Based Data Capture
WHO	World Health Organization

